3.8.4 Immunogenicity Assessment

All subjects must have samples for anti-opebacan antibody analysis drawn at prescreening. Samples will also be collected at Day 28 ± 3 days to detect whether subjects have developed anti-opebacan antibodies. In addition, donors who consent must have samples drawn for anti-opebacan antibody analysis prior to stem cell harvest.

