After all subjects in a dose group have completed study procedures through Day 28, all available safety information will be reviewed by the DSMB. Dosing may begin for the next dose group at the next higher dose level if no more than one subject in the previous group has experienced a DLT (see Section 3.3.2 for the definition of DLT) and, in the opinion of the DSMB, there are no clinically significant safety concerns at the previous dose level.

All subjects will have disease status, performance score, and cumulative aGvHD status confirmed on Day 100 (± 14 days) by clinic visit, if possible, or by phone. Safety will be assessed by pre- and post-treatment serial measurements of vital signs and clinical laboratory assessments and by the recording of adverse clinical events, with an emphasis on infectious and non-infectious regimen-related toxicities. PK data will be collected and analyzed to determine dose/duration relationships and to explore preliminary correlations of PK data with demographic information, clinical course through transplant, occurrence of transplant regimen related toxicities including aGvHD, and laboratory markers of inflammation. Figure 1 outlines the study design.

Figure 1

- The visit window for Days 21, 28, 42, and 49 is \pm 3 days. The visit window for Day 100 is \pm 14 days.
- IV infusion with opebacan will begin on Day -1, 18 to 36 hours prior to the HSCT. Prior to opebacan dosing, the Principal Investigator or designee must confirm and document that the subject meets all eligibility criteria for the HSCT and that the initiation of study drug administration will precede donor cell administration by 18 to 36 hours. Subjects whose conditioning regimen consists of chemotherapy only will receive a continuous opebacan infusion following completion of chemotherapy treatment on Day -1. Subjects whose conditioning regimen includes total body irradiation (TBI) will have three 1-hour interruptions in their opebacan infusions (one on Day -1 and two on Day 0) to accommodate TBI treatment. Following the final interruption on Day 0, the infusion must be restarted at least 2 hours prior to the HSCT.
- The HSCT will be performed on Day 0, 18 to 36 hours following initiation of opebacan treatment, and no less than 18 hours after the completion of chemotherapy treatment.
- All subjects will have disease status, performance score, and cumulative aGvHD status confirmed on Day 100 (± 14 days) by clinic visit, if possible, or by phone.

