5.5 Type and Duration of Follow-up After Adverse Events

5.5.1 Post Treatment Follow-up

All subjects receiving any amount of drug will be followed until Day 100. All protocoldefined AEs occurring during the treatment and post-treatment periods should be fully evaluated by the Investigator, recorded on the appropriate pages of the CRF, and documented in the subjects' files.

SAEs that occur after the subject has completed the clinical trial generally need not to be reported unless the Investigator believes the event may be related to the administration of study drug.

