6.5.4 Antibody Response to Opebacan

The proportion of subjects with an antibody response to opebacan will be summarized by dose group.

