Appendix 2: Study BPSC030 PK Sampling Schedule¹

Study Day	sscreen			-1			0	1			2			3			6			7	10			13			14	100
Minutes ²	Pre	Pre	30	45	90	270	1440	2880	EOI	15	30	60	240	1440	EOI	15	30	60	240	1440		EOI	15	30	60	240	1440	
Group 1	X^3	X^3	X	X	X	X	X	X	X	X	X	X	X	X														X
Group 2	X^3	X^3	X	X	X	X	X	X	X	X	X	X	X	X														X
Group 3	X^3	X^3	X	X	X	X	X	X	X	X	X	X	X	X														X
Group 4	X^3	X^3	X	X	X	X	X	X							X	X	X	X	X	X								X
Group 5	X^3	X^3	X	X	X	X	X	X							X^4						X	X	X	X	X	X	X	X
Donor	X^3																											

¹ PK sample must be drawn from a different vein than that used for opebacan administration.

For Days –1, 0, and 1, sampling time is shown in minutes following initiation of opebacan treatment. For Days 2 and 3 (Groups 1, 2, and 3), Days 6 and 7 (Group 4), and Days 13 and 14 (Group 5), sampling times are shown in minutes following the end of infusion (EOI). The "EOI" sample must be drawn within one hour prior to the end of the opebacan infusion. The acceptable windows for the other PK draws are as follows: 15 ± 5 minutes, 30 ± 5 minutes, 45 ± 5 minutes, 60 ± 10 minutes, 90 ± 15 minutes, 240 ± 30 minutes, 270 ± 30 minutes, 1440 ± 60 minutes, and 2880 ± 60 minutes.

³ The PK samples for the donor and subject at prescreen and for the subject at predose on Day –1 are used for measuring the level of endogenous BPI.

The PK sample for Group 5 subjects on Day 6 is drawn along with other blood draws on that day. Though it appears in the EOI column, the infusion for this dose group does not end until Day 13.

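### Anti-opebacan antibody is measured after treatment only at Day 28, so later responses would be missed, and time since end of infusion is shorter in Groups 4 and 5

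*Supplement*

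**What the plan says.** Section 3.8.4 sets the baseline: "All subjects must have samples for anti-opebacan antibody analysis drawn at prescreening". It then adds the one post-treatment sample: "Samples will also be collected at Day 28 ± 3 days to detect whether subjects have developed anti-opebacan antibodies". It also asks for a donor baseline: "donors who consent must have samples drawn for anti-opebacan antibody analysis prior to stem cell harvest". The visit lists in section 4.3.2 and the antibody row of Appendix 1 agree that Day 28 is the only post-treatment time point.

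The analysis in section 6.5.4 is one sentence: "The proportion of subjects with an antibody response to opebacan will be summarized by dose group". Section 6.0 rules out formal testing.

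Exposure starts on the same day in every group: "IV infusion with opebacan will begin on Day -1, 18 to 36 hours prior to the HSCT". It ends on different days. Footnote 2 of Appendix 2 places the end-of-infusion samples and those 24 hours later as follows: "For Days 2 and 3 (Groups 1, 2, and 3), Days 6 and 7 (Group 4), and Days 13 and 14 (Group 5". Footnote 4 confirms for Group 5 that "the infusion for this dose group does not end until Day 13".

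On follow-up, section 5.5.1 says: "All subjects receiving any amount of drug will be followed until Day 100". The Day 100 lists in section 4.3.2 include PK, chemistry, coagulation, blood count, LPS/LBP and soluble markers. They do not include antibody.

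**The concern.** Section 6.5.4 can report only what the one sample detects, and the timing of that sample raises two issues.

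First, it is taken early in immune recovery. Section 3.2.1.2 says conditioning is meant to destroy lymphoid and hematopoietic cells. Section 3.3.4 accepts engraftment as late as Day 28, and section 3.6.6.2 lists immunosuppressives as acceptable. A response that appears after about Day 31 cannot be found, although subjects remain in the study for some ten weeks more.

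Second, the sampling day is fixed while infusion length is escalated. Subjects given longer infusions are therefore tested sooner after their last exposure. A difference between Groups 4–5 and Groups 1–3, or the lack of one, would mix the effect of regimen with that of follow-up length.

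At stake is whether a row of low or zero proportions can be interpreted. Section 1.3 already describes the drug as having low immunogenicity in other populations, so zeros at Day 28 could be taken as confirmation in a population where it has not been given before.

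**Working it through.** The documents give no precision or power figure for immunogenicity, so there is none to reproduce.

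**Intervals.** Inputs: infusion starts on Day −1 (section 3.1) and ends on Day 2, 6 or 13 (Appendix 2). Antibody is drawn at Day 28 ± 3 (section 3.8.4), and the last visit is Day 100 ± 14 (section 3.1). Interval = sampling day − end-of-infusion day, with the range from the visit window.

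| Group | End of infusion | To Day 28 (range) | To Day 100 (range) |
|---|---|---|---|
| 1–3 | Day 2 | 28 − 2 = 26 (23–29) | 100 − 2 = 98 (84–112) |
| 4 | Day 6 | 28 − 6 = 22 (19–25) | 100 − 6 = 94 (80–108) |
| 5 | Day 13 | 28 − 13 = 15 (12–18) | 100 − 13 = 87 (73–101) |

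- From first exposure to Day 28: 28 − (−1) = 29 days in every group.
- Group 5 against Groups 1–3, from end of infusion: 15/26 = 58%. The two ranges (12–18 and 23–29) do not overlap.
- Spread between groups: 26 − 15 = 11 days, which is 11/26 = 42% of the longest interval at Day 28. At Day 100 it would be 11/98 = about 11%.

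**Engraftment against sampling.** The sampling window is Day 25 to Day 31. A subject whose engraftment is dated Day 28 counts as a success under section 3.3.4, yet could be sampled up to three days before it.

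**Who contributes a result.** Sections 3.5 and 4.5.1 replace subjects who lack 7 days of assessments after infusion. The last such day is 2 + 7 = 9, 6 + 7 = 13 or 13 + 7 = 20, always before the window opens on Day 25. The early-termination list has no antibody sample. A subject can therefore be treated, not replaced, and have no post-treatment antibody result.

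**What zero positives would show.** The exact one-sided 95% upper bound for 0/n is 1 − 0.05^(1/n).

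- n = 6 (one group): 39.3%.
- n = 30 (all groups pooled): 9.5%.

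These bounds assume that the Day 28 sample detects every eventual responder. The documents give no such detection share, so the shares below are assumptions shown as a range. If the share is s, the bound on the true rate is the figure above divided by s, capped at 100%.

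| Assumed s | Bound, 0/6 | Bound, 0/30 |
|---|---|---|
| 100% | 39% | 9.5% |
| 75% | 52% | 13% |
| 50% | 79% | 19% |
| 25% | 100% | 38% |

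At an assumed true rate of 20%, the chance of seeing 0/6 is (1 − 0.20 × s)^6, which is 26%, 38%, 53% and 74% for the same four shares.

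**The case against.** The measure is descriptive, immunogenicity is not among the four objectives in section 2.0, and six subjects per group already prevent a claim of no response. That stands: with perfect detection, 0/6 still leaves a bound of 39%. Pooling reduces that limit but does not remove the timing limit, as the 0/30 column shows under the assumed shares.

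Day 28 also has a visible rationale. Its assessments are required for all subjects whether or not discharged, and the safety review for escalation follows it. Day 100 may be done by phone. This is a good reason to keep Day 28, but not a reason to stop there.

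Three stronger readings are tempting, and the documents do not support them.

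- *The dose groups are not comparable.* All groups have the same time since first exposure, and Groups 1–3 match on both measures. Only time since last exposure differs, and only for Groups 4 and 5.
- *The proportion is biased towards zero, most of all in Group 5.* The documents give no antibody kinetics, no degree of blunting and no assay sensitivity; section 3.9.2 says the assay is still to be developed. Group 5 also has a larger total dose than Group 3 (172/40 = 4.3 times) and longer exposure, and nothing shows which influence would prevail.
- *The trial is set up to declare the drug non-immunogenic.* Section 6.5.4 promises only a summary, and no section commits to that conclusion.

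Two cautions on the evidence also stand. Engraftment here is a neutrophil criterion and does not describe antibody-producing capacity. The documents do not show that a response would have appeared by Day 100 either.

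**Conclusion.** The point holds in a limited form. One post-treatment sample, at a time when engraftment may be recent or still to come, cannot detect later responses, although follow-up runs to Day 100. The interval since end of infusion is 26, 22 and 15 days, so Groups 4–5 are set beside Groups 1–3 at unequal post-exposure follow-up. These statements rest only on the protocol's own schedule. How many responses would be missed, and whether any group difference would be raised or lowered, cannot be determined from the documents; the detection shares in the working are illustrative. A negative at Day 28 alone is inconclusive. This is a cheap improvement to a secondary descriptive measure, not a flaw in the main design.

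**What to change.** Keep Day 28. Add an anti-opebacan antibody sample to the existing Day 100 (± 14) draw in three places: section 3.8.4, the Day 100 lists in section 4.3.2 for all groups, and the antibody row of Appendix 1. Because that column of Appendix 1 also serves visits at diagnosis of grade 2 or higher aGvHD, a footnote should say whether the new sample applies to Day 100 only.

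In section 6.5.4, report the Day 28 and Day 100 proportions separately by dose group, each with the number tested and the days since end of infusion. State that a negative at Day 28 alone will not be read as absence of a response.

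The cost is one tube and one assay per subject: about 30 at planned accrual (6 × 5), 30 to 40 at the expected enrollment in the synopsis, and 60 at its maximum. The downside is missing Day 100 values for subjects followed by phone or who die earlier; giving the number tested makes this visible.

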3.9 Assay Methods

3.9.1 Pharmacokinetics Assay

A sandwich ELISA was developed for the measurement of opebacan in plasma. The ELISA utilizes an affinity-purified rabbit anti-BPI antibody for solid-phase capture and a biotin-labeled rabbit anti-BPI antibody (followed by streptavidin-alkaline phosphatase) as the detector. A standard curve is plotted as A_{405} versus concentration. A four-parameter fit is performed and concentrations are determined for samples and controls by interpolation from the standard curve.

3.9.2 Immunological Assay

An immunoassay will be developed for the measurement of anti-opebacan antibodies in human plasma. The assay will utilize control plasma from either a primate and/or a non-primate species.

4.0 STUDY OPERATIONS AND EVALUATIONS

4.1 Overview

To decrease variability in this study, reassessments requiring interpretation or manual measurements should, as consistently as possible, be made by the same individual performing the original assessment.

4.2 Reporting and Recording of Data

Case Report Forms (CRFs) will be supplied by XOMA and should be completed according to the instructions provided in the CRF Completion Guidelines and ICH/GCP Guidelines.

A CRF must be completed for each subject enrolled under this protocol. Information collected on the screen failure subjects will include subject initials, date of birth, and the reason the subject was not enrolled.

All information collected in the CRF must be verifiable in the source documents. Source documents for this trial may include hospital records, clinic records, and any study-specific worksheets or laboratory result reporting documents. Subject medical records must contain reference to the study title and assigned subject identification number. The signed consent form must be filed with the subject's medical record.

CRF completion must be kept current to reflect subject status during the course of the trial. All CRF data must be reviewed, signed and dated by the Principal Investigator.

All CRFs should be completed in a neat and legible manner to ensure accurate interpretation of data. When making changes or corrections, cross out the original entry with a single line, and initial and date the change. DO NOT ERASE, OVERWRITE, OR USE CORRECTION FLUID ON THE ORIGINAL CRF.

CRF pages will be double data entered at XOMA, after which the data may be manually or electronically reviewed by the clinical team. Any resulting data queries will be sent back to the site for resolution.

Study subjects will be identified by subject ID number, initials, and date of birth. Subject names or other personal identification (e.g., subject social security number) must be blacked out on any documents submitted to XOMA or their designee, with subject ID number, initials and protocol number transcribed onto the upper right hand corner of each document page.

Information on donors who consent, including the donor ID number and the data from assessments performed on the donor, will be entered on the appropriate pages of the CRF of the subject who received that donor's stem cells.

4.3 Study Assessments

Study assessments are shown in the Schedule of Assessments (Appendix 1). Routine laboratory analyses, including chemistries, CBC, coagulation measures, and urinalysis will be performed locally at the study sites. Surface markers requiring same day analysis (e.g., TLR4) will also be processed and analyzed locally, though in some circumstances these samples may be frozen, batched and sent to a central lab. All other samples will be analyzed at a central lab.

The following assessments will be performed daily from Day –1 until Day 49 or until the subject is released from the hospital, whichever occurs first:

- Metabolic assessment (Intake and output [I&O] and total days of parenteral nutrition [TPN] only). Assessments requiring daily totals should be measured by calendar day (i.e., from midnight to midnight) unless otherwise specified by institutional standard practice.
- Vital signs including pulse, blood pressure (systolic/diastolic), respiratory rate, and temperature taken in the morning (i.e., the first waking set of vital signs). If a subject experiences an SAE, vital signs must be taken more frequently, per standard institutional practice.

In addition, the oral mucositis score must be recorded at prescreening and then daily from Day –1 through Day 7 (see Appendix 5 for grading scale). After Day 7, the oral mucositis score must be recorded daily until the condition resolves to grade 0. If oral mucositis reappears after resolving, daily assessments must be reinstituted through Day 49 or until the subject is released from the hospital, whichever occurs first.

All assessments scheduled on Days 14, 21, and 28 must be performed for all subjects whether or not the subjects have been discharged from the hospital. Assessments scheduled on Days 35, 42 and 49 will be performed only for those subjects who are still hospitalized on those days. Note that assessments scheduled between Day 14 and Day 49 (excluding Days 21, 28, 35, and 42) are not shown in the table for Appendix 1 (Study BPSC030 Schedule of Assessments), though they are mentioned in the footnotes for the assessments that are affected (i.e., Footnote 14 [metabolic assessment], Footnote 15 [vital signs], and Footnote 21 [oral mucositis]).

Several of the assessments performed during this study are considered "over and above" those normally performed as part of routine patient care for HSCT procedures. These special assessments are as follows:

- DNA testing (SNPs for markers such as TLR and TNF) at select sites only
- Opebacan blood levels (PK assays)
- Inflammatory markers such as LPS and LBP
- LPS-induced TNF and IL-6 at select sites only

• Soluble markers that may include, but may not be limited to, sCD14, TNF-RI, IL-1, IL-6, IL-8, IL-10, IL-12, and CRP

- Surface markers at select sites only; may include, but may not be limited to, TLR4 and mCD14
- Cardiac serology including CPK-MB, troponin T, and troponin I
- Anti-opebacan antibody response

4.3.1 Screening Assessments

Before any screening evaluations or measurements are performed, subjects must be fully informed and sign a XOMA/IRB-approved informed consent form for participation in this study. All screening evaluations must be performed prior to the start of study drug dosing (Day -1).

Prescreening (Within 30 Days of Hospital Admission for Conditioning, HSCT)

- Signed XOMA/IRB-approved informed consent
- Review of inclusion and exclusion criteria
- Demographic information (sex, age, race/ethnicity)
- Medical history, including virology and serology status
- HIV antibody
- ECG
- Urine or serum pregnancy test for women of childbearing potential only
- DNA testing (SNPs for markers such as TLR and TNF) at select sites only
- Review and recording of concomitant medications
- PK sample for measuring level of endogenous BPI
- Laboratory evaluations:
 - Chemistries: Sodium, potassium, chloride, bicarbonate, glucose, BUN, creatinine, calcium, phosphorus, magnesium, bilirubin (total, and direct if bilirubin > 2.0 mg/dL), albumin, ALT, AST, LDH, alkaline phosphatase, and total protein
 - Coagulation: PT, PTT, fibringen, and D-Dimers (or FDP or FSP)
 - Urinalysis: Chemistry and microscopic examination
 - Hematology: CBC with differential and platelet count
- Physical examination

Vital signs including pulse, blood pressure (systolic/diastolic), respiratory rate, and temperature taken in the morning (i.e., the first waking set of vital signs). If a subject experiences an SAE, vital signs must be taken more frequently, per standard institutional practice. (Note: Vital signs must be recorded daily from prescreening through Day 49 or until the subject is released from the hospital, whichever occurs first.)

- LPS and LBP
- LPS-induced TNF and IL-6 at select sites only
- Oral mucositis score (see Appendix 5)
- Cardiac serology (CPK-MB, cardiac troponin T, and troponin I)
- LVEF by ECHO or MUGA
- Anti-opebacan antibody response

Day -3 (All Subjects)

- LPS
- Surface markers at select sites only; may include, but may not be limited to, TLR4 and mCD14

Final Screening (Day -1)

The following final screen assessments must be completed prior to dosing with opebacan:

- Review of inclusion and exclusion criteria
- Interim medical history
- Metabolic assessment. The subject or legal guardian will be asked to provide the subject's recent dietary history.
- Review and recording of concomitant medications
- Confirmation and documentation by the Principal Investigator or designee that the subject meets all eligibility criteria for the HSCT and that the initiation of study drug administration will precede donor cell administration by the appropriate 18 to 36 hours
- Approval of initiation of drug administration by the Principal Investigator or designee

4.3.2 Assessments for Treatment and Follow-up Period

If a subject has a clinically significant abnormal laboratory test value that was not present at baseline (Day -1 prior to opebacan dosing), the test will be repeated and the subject will be followed until the test value has returned to the baseline range or the Investigator has determined that the abnormality is chronic or stable.

4.3.2.1 Assessments for Treatment and Follow-up Period: Dose Groups 1, 2, and 3

Day -1 (Dose Groups 1, 2, and 3)

- Interim medical history (predose)
- Adverse events (Note: The "signs and symptoms inventory" CRF page must be completed predose and all AEs collected postdose.)
- Review and recording of concomitant medications
- PK sample (predose and 30, 45, 90, and 270 minutes after the start of infusion). Note: PK sample must be drawn from a different vein than that used for opebacan administration.
- Laboratory evaluations (predose):
 - Chemistries: Sodium, potassium, chloride, bicarbonate, glucose, BUN, creatinine, calcium, phosphorus, magnesium, bilirubin (total, and direct if bilirubin > 2.0 mg/dL), albumin, ALT, AST, LDH, alkaline phosphatase, and total protein
 - Coagulation: PT, PTT, fibringen, and D-Dimers (or FDP or FSP)
 - Urinalysis: Chemistry and microscopic examination
 - Hematology: CBC with differential and platelet count
- Metabolic assessment (Caloric source documentation including volume and type
 for all fluids and nutritional sources, intake and output [I&O], and total days of
 parenteral nutrition [TPN]). Assessments requiring daily totals should be
 measured by calendar day (i.e., from midnight to midnight) unless otherwise
 specified by institutional standard practice.
- Vital signs including pulse, blood pressure (systolic/diastolic), respiratory rate, and temperature. Temperature is measured twice: predose (within one hour prior to the start of infusion) and postdose (within four hours after the start of infusion). In addition, body weight must be measured predose to calculate the study drug dose. If a subject experiences an SAE, vital signs must be taken more frequently, per standard institutional practice.
- Fever (T_{max}) measured for two separate periods: predose (within one hour prior to the start of infusion) and postdose (within four hours after the start of infusion).
- LPS and LBP (predose)

- LPS-induced TNF and IL-6 (predose) at select sites only
- Soluble markers (predose) that may include, but may not be limited to, sCD14, TNF-RI, IL-1, IL-6, IL-8, IL-10, IL-12, and CRP
- Surface markers (predose) at select sites only; may include, but may not be limited to, TLR4 and mCD14
- Oral mucositis score (predose; see Appendix 5)
- Cardiac serology (CPK-MB, cardiac troponin T, and troponin I) (predose)
- LVEF by ECHO or MUGA (predose)
- Performance score (predose using Karnofsky criteria; see Appendix 3)
- Initiation of opebacan dosing. Subjects whose conditioning regimen includes TBI will have their opebacan infusion interrupted for a 1-hour TBI treatment.

Day 0 (Day of HSCT) (Dose Groups 1, 2, and 3)

- Adverse events
- Concomitant medications
- PK sample (24 hours after start of infusion). Note: PK sample must be drawn from a different vein than that used for opebacan administration.
- Laboratory evaluations:
 - Hematology: CBC with differential and platelet count
- Metabolic assessment (Caloric source documentation including volume and type
 for all fluids and nutritional sources, intake and output [I&O], and total days of
 parenteral nutrition [TPN]). Assessments requiring daily totals should be
 measured by calendar day (i.e., from midnight to midnight) unless otherwise
 specified by institutional standard practice.
- Vital signs including pulse, blood pressure (systolic/diastolic), respiratory rate, and temperature taken in the morning (i.e., the first waking set of vital signs). If a subject experiences an SAE, vital signs must be taken more frequently, per standard institutional practice.
- Fever (T_{max})
- LPS and LBP
- Soluble markers that may include, but may not be limited to, sCD14, TNF-RI, IL-1, IL-6, IL-8, IL-10, IL-12, and CRP
- Surface markers at select sites only; may include, but may not be limited to, TLR4 and mCD14
- Oral mucositis score (see Appendix 5)

• Continuation of opebacan dosing. Subjects whose conditioning regimen includes TBI will have their opebacan infusion interrupted for 1-hour TBI treatments twice on Day 0 prior to the HSCT procedure. The HSCT will take place after the opebacan infusion has been restarted for at least 2 hours.

Day 1 (Dose Groups 1, 2, and 3)

- Adverse events
- Concomitant medications
- PK sample. Note: PK sample must be drawn from a different vein than that used for opebacan administration.
- Metabolic assessment (Intake and output [I&O] and total days of parenteral nutrition [TPN] only). Assessments requiring daily totals should be measured by calendar day (i.e., from midnight to midnight) unless otherwise specified by institutional standard practice.
- Vital signs including pulse, blood pressure (systolic/diastolic), respiratory rate, and temperature taken in the morning (i.e., the first waking set of vital signs). If a subject experiences an SAE, vital signs must be taken more frequently, per standard institutional practice.
- Fever (T_{max})
- Oral mucositis score (see Appendix 5)
- Cardiac serology (CPK-MB, cardiac troponin T, and troponin I)
- Continuation of opebacan dosing

Day 2 (Dose Groups 1, 2, and 3)

Unless otherwise noted, the following assessments should be performed immediately after the end of the opebacan infusion:

- Adverse events
- Concomitant medications
- PK sample (prior to end of infusion and 15, 30, 60, and 240 minutes after the end of infusion). Note: PK sample must be drawn from a different vein than that used for opebacan administration.
- Laboratory evaluations
 - Hematology: CBC with differential and platelet count
- Metabolic assessment (Intake and output [I&O] and total days of parenteral nutrition [TPN] only). Assessments requiring daily totals should be measured by

- calendar day (i.e., from midnight to midnight) unless otherwise specified by institutional standard practice.
- Vital signs including pulse, blood pressure (systolic/diastolic), respiratory rate, and temperature taken in the morning (i.e., the first waking set of vital signs). If a subject experiences an SAE, vital signs must be taken more frequently, per standard institutional practice.
- Fever (T_{max})
- LPS and LBP
- Soluble markers that may include, but may not be limited to, sCD14, TNF-RI, IL-1, IL-6, IL-8, IL-10, IL-12, and CRP
- Surface markers at select sites only; may include, but may not be limited to, TLR4 and mCD14
- Oral mucositis score (see Appendix 5)
- End of opebacan dosing

Day 3 (Dose Groups 1, 2, and 3)

- Adverse events
- Concomitant medications
- PK sample (24 hours after the end of infusion). Note: PK sample must be drawn from a different vein than that used for opebacan administration.
- Laboratory evaluations:
 - Chemistries: Sodium, potassium, chloride, bicarbonate, glucose, BUN, creatinine, calcium, phosphorus, magnesium, bilirubin (total, and direct if bilirubin > 2.0 mg/dL), albumin, ALT, AST, LDH, alkaline phosphatase, CPK (with MB fraction), and total protein
 - Coagulation: PT, PTT, fibringen, and D-Dimers (or FDP or FSP)
 - Urinalysis: Chemistry and microscopic examination
 - Hematology: CBC with differential and platelet count
- Metabolic assessment (Caloric source documentation including volume and type
 for all fluids and nutritional sources, intake and output [I&O], and total days of
 parenteral nutrition [TPN]). Assessments requiring daily totals should be
 measured by calendar day (i.e., from midnight to midnight) unless otherwise
 specified by institutional standard practice.
- Vital signs including pulse, blood pressure (systolic/diastolic), respiratory rate, and temperature taken in the morning (i.e., the first waking set of vital signs). If a subject experiences an SAE, vital signs must be taken more frequently, per standard institutional practice.

- Fever (T_{max})
- Oral mucositis score (see Appendix 5)

Day 4 (Dose Groups 1, 2, and 3)

- Adverse events
- Concomitant medications
- Metabolic assessment (Intake and output [I&O] and total days of parenteral nutrition [TPN] only). Assessments requiring daily totals should be measured by calendar day (i.e., from midnight to midnight) unless otherwise specified by institutional standard practice.
- Vital signs including pulse, blood pressure (systolic/diastolic), respiratory rate, and temperature taken in the morning (i.e., the first waking set of vital signs). If a subject experiences an SAE, vital signs must be taken more frequently, per standard institutional practice.
- Fever (T_{max})
- LPS and LBP
- Oral mucositis score (see Appendix 5)
- Cardiac serology (CPK-MB, cardiac troponin T, and troponin I)

Day 5 (Dose Groups 1, 2, and 3)

- Adverse events
- Concomitant medications
- Metabolic assessment (Intake and output [I&O] and total days of parenteral nutrition [TPN] only). Assessments requiring daily totals should be measured by calendar day (i.e., from midnight to midnight) unless otherwise specified by institutional standard practice.
- Vital signs including pulse, blood pressure (systolic/diastolic), respiratory rate, and temperature taken in the morning (i.e., the first waking set of vital signs). If a subject experiences an SAE, vital signs must be taken more frequently, per standard institutional practice.
- Fever (T_{max})
- Oral mucositis score (see Appendix 5)

Day 6 (Dose Groups 1, 2, and 3)

Adverse events

- Concomitant medications
- Metabolic assessment (Intake and output [I&O] and total days of parenteral nutrition [TPN] only). Assessments requiring daily totals should be measured by calendar day (i.e., from midnight to midnight) unless otherwise specified by institutional standard practice.
- Vital signs including pulse, blood pressure (systolic/diastolic), respiratory rate, and temperature taken in the morning (i.e., the first waking set of vital signs). If a subject experiences an SAE, vital signs must be taken more frequently, per standard institutional practice.
- Fever (T_{max})
- LPS and LBP
- Oral mucositis score (see Appendix 5)

Day 7 (Dose Groups 1, 2, and 3)

- Adverse events
- Concomitant medications
- Laboratory evaluations:
 - Hematology: CBC with differential and platelet count
- Metabolic assessment (Caloric source documentation including volume and type
 for all fluids and nutritional sources, intake and output [I&O], and total days of
 parenteral nutrition [TPN]). Assessments requiring daily totals should be
 measured by calendar day (i.e., from midnight to midnight) unless otherwise
 specified by institutional standard practice.
- Vital signs including pulse, blood pressure (systolic/diastolic), respiratory rate, and temperature taken in the morning (i.e., the first waking set of vital signs). If a subject experiences an SAE, vital signs must be taken more frequently, per standard institutional practice.
- Fever (T_{max})
- Soluble markers that may include, but may not be limited to, sCD14, TNF-RI, IL-1, IL-6, IL-8, IL-10, IL-12, and CRP
- Surface markers at select sites only; may include, but may not be limited to, TLR4 and mCD14
- Oral mucositis score (see Appendix 5)
- LVEF by ECHO or MUGA
- Grading for aGVHD (see Appendix 4)
- Performance score (Karnofsky criteria; see Appendix 3)

Day 8 (Dose Groups 1, 2, and 3)

- Adverse events
- Concomitant medications
- Metabolic assessment (Intake and output [I&O] and total days of parenteral nutrition [TPN] only). Assessments requiring daily totals should be measured by calendar day (i.e., from midnight to midnight) unless otherwise specified by institutional standard practice.
- Vital signs including pulse, blood pressure (systolic/diastolic), respiratory rate, and temperature taken in the morning (i.e., the first waking set of vital signs). If a subject experiences an SAE, vital signs must be taken more frequently, per standard institutional practice.
- Fever (T_{max})
- LPS and LBP
- Oral mucositis score recorded daily until condition resolves to grade 0 (see Appendix 5)
- Cardiac serology (CPK-MB, cardiac troponin T, and troponin I)

Day 9 (Dose Groups 1, 2, and 3)

- Adverse events
- Concomitant medications
- Metabolic assessment (Intake and output [I&O] and total days of parenteral nutrition [TPN] only). Assessments requiring daily totals should be measured by calendar day (i.e., from midnight to midnight) unless otherwise specified by institutional standard practice.
- Vital signs including pulse, blood pressure (systolic/diastolic), respiratory rate, and temperature taken in the morning (i.e., the first waking set of vital signs). If a subject experiences an SAE, vital signs must be taken more frequently, per standard institutional practice.
- Fever (T_{max})
- Oral mucositis score recorded daily until condition resolves to grade 0 (see Appendix 5)

Day 10 (Dose Groups 1, 2, and 3)

Adverse events

- Concomitant medications
- Laboratory evaluations:
 - Hematology: CBC with differential and platelet count
- Metabolic assessment (Caloric source documentation including volume and type for all fluids and nutritional sources, intake and output [I&O], and total days of parenteral nutrition [TPN]). Assessments requiring daily totals should be measured by calendar day (i.e., from midnight to midnight) unless otherwise specified by institutional standard practice.
- Vital signs including pulse, blood pressure (systolic/diastolic), respiratory rate, and temperature taken in the morning (i.e., the first waking set of vital signs). If a subject experiences an SAE, vital signs must be taken more frequently, per standard institutional practice.
- Fever (T_{max})
- LPS and LBP
- Oral mucositis score recorded daily until condition resolves to grade 0 (see Appendix 5)

Day 11 (Dose Groups 1, 2, and 3)

- Adverse events
- Concomitant medications
- Metabolic assessment (Intake and output [I&O] and total days of parenteral nutrition [TPN] only). Assessments requiring daily totals should be measured by calendar day (i.e., from midnight to midnight) unless otherwise specified by institutional standard practice.
- Vital signs including pulse, blood pressure (systolic/diastolic), respiratory rate, and temperature taken in the morning (i.e., the first waking set of vital signs). If a subject experiences an SAE, vital signs must be taken more frequently, per standard institutional practice.
- Fever (T_{max})
- Oral mucositis score recorded daily until condition resolves to grade 0 (see Appendix 5)

Day 12 (Dose Groups 1, 2, and 3)

- Adverse events
- Concomitant medications

• Metabolic assessment (Intake and output [I&O] and total days of parenteral nutrition [TPN] only). Assessments requiring daily totals should be measured by calendar day (i.e., from midnight to midnight) unless otherwise specified by institutional standard practice.

- Vital signs including pulse, blood pressure (systolic/diastolic), respiratory rate, and temperature taken in the morning (i.e., the first waking set of vital signs). If a subject experiences an SAE, vital signs must be taken more frequently, per standard institutional practice.
- Fever (T_{max})
- Oral mucositis score recorded daily until condition resolves to grade 0 (see Appendix 5)

Day 13 (Dose Groups 1, 2, and 3)

- Adverse events
- Concomitant medications
- Metabolic assessment (Intake and output [I&O] and total days of parenteral nutrition [TPN] only). Assessments requiring daily totals should be measured by calendar day (i.e., from midnight to midnight) unless otherwise specified by institutional standard practice.
- Vital signs including pulse, blood pressure (systolic/diastolic), respiratory rate, and temperature taken in the morning (i.e., the first waking set of vital signs). If a subject experiences an SAE, vital signs must be taken more frequently, per standard institutional practice.
- Fever (T_{max})
- Oral mucositis score recorded daily until condition resolves to grade 0 (see Appendix 5)

Day 14 (Dose Groups 1, 2, and 3)

- Adverse events
- Concomitant medications
- Metabolic assessment (Caloric source documentation including volume and type
 for all fluids and nutritional sources, intake and output [I&O], and total days of
 parenteral nutrition [TPN]). Assessments requiring daily totals should be
